Assessment	Name	Items	Concepts	Approx. Duration (min)	PRO, ObsRO, PerfO, Behavior	Timing	Location
SDMT/ eSDMT	Symbol Digit Modalities Test	Max number in 90 seconds	Cognitive	5	PerfO	SDMT at baseline and Weeks 5, 21, 37, 53, 69, 85, and 101 and ETT visits	In-clinic
						eSDMT monthly + at clinic visits (screening, baseline, Weeks 5, 53, 101, and ETT)	Roche HD mobile app (eSDMT)
SMDDS	Symptoms of Major Depressive Disorder Scale	16	Depression, anxiety, irritability, sleep	10	PRO	Baseline and Weeks 13, 29, 45, 61, 77, 93, and 101	In-clinic
SWR/eSWR	Stroop Word Reading Test	Max numbers in 45 seconds	Cognitive	5	PerfO	SWR at baseline and Weeks 5, 21, 37, 53, 69, 85, and 101 and ETT visits	In-clinic
						eSWR monthly + at clinic visits (screening, baseline, Weeks 5, 53, and 101 and ETT)	Roche HD mobile app (eSWR)
WPAI	Work Productivity and Activity Impairment	6	Work productivity	5	PRO + ObsRO	Baseline and then monthly	Roche HD mobile app and electronic device

app=application; ETT=early treatment termination; HD=Huntington disease; ObsRO=observer-reported outcome; PerfO=performance outcome;
PRO=patient-reported outcome.

Appendix 4 Clinical Assessments Order and Duration for Patients Enrolled after Implementation of Protocol Version 4

Table 1 Screening Visit Clinical Assessments

Block	Assessments	Total Duration (minutes)	Site Staff Responsible
1	Diagnostic Confidence Level ^a Huntington's Disease Daily Activities Scale Independence Scale MoCA C-SSRS	~60	Qualified study physician
Break (if needed)		~20-30	
2	Roche HD mobile application	~20	Qualified study personnel

C-SSRS=Columbia-Suicide Severity Rating Scale; DCL = Diagnostic Confidence Level; HD=Huntington disease; MoCA=Montreal Cognitive Assessment; TMS = Total Motor Score.

^a The DCL will be assessed at screening only (i.e., without the full TMS assessment). The TMS scale will be assessed (excluding the DCL) at all other timepoints.

Appendix 4: Clinical Assessments Order and Duration for Patients Enrolled after Implementation of Protocol Version 4 (cont.)

Table 2 Baseline and Week 101 Clinical Assessments (for Primary Analysis)

Block	Assessments	Total Duration (minutes)	Site Staff Responsible
1	UHDRS Functional Assessment Independence Scale Total Functional Capacity Scale Total Motor Score (without Diagnostic Confidence Level) Columbia-Suicide Severity Rating Scale Clinical Global Impression—Severity Clinical Global Impression—Change (post-baseline visits only)	~60	Qualified study physician
	Break (if needed)	~20–30	
2	Symbol Digit Modalities Test Stroop Word Reading Test MoCA	~20	Qualified study personnel
	Break (if needed)	~10	
3 ^a	Apathy Evaluation Scale (patient and companion) Symptoms of Major Depressive Disorder Scale	~20	Qualified study personnel
	Break (if needed)	~10–20	
4 ^a	Neuro-QoL Cognition Function Short Form EuroQol 5-Dimension, 5-Level Questionnaire (patient and companion) Health Utilities Index (companion: self and proxy) Patient/Companion-reported Global Impression—Severity Patient/Companion-reported Global Impression—Change (post-baseline visits only)	~20	Qualified study personnel
	Break (if needed)	~10–20	
5 ^a	Roche HD mobile application	~20	Qualified study personnel

HD=Huntington disease; MoCA=Montreal Cognitive Assessment; Neuro-QoL=Quality of Life in Neurological Disorders; UHDRS=Unified Huntington's Disease Rating Scale.

^a At the baseline visit and at Week 101, Blocks 3, 4, and 5 can be completed on the same day after Blocks 1 and 2, or on the following day, but must be completed predose at the baseline visit.

Appendix 4: Clinical Assessments Order and Duration for Patients Enrolled after Implementation of Protocol Version 4 (cont.)

Table 3 Follow-Up Clinical Assessments at Weeks 5, 21, 37, 53, 69, and 85

Block	Assessments	Total Duration (minutes)	Site Staff Responsible
1	UHDRS Functional Assessment Independence Scale Total Functional Capacity Scale Total Motor Score (without Diagnostic Confidence Level) Columbia-Suicide Severity Rating Scale Clinical Global Impression—Severity Clinical Global Impression—Change	~60	Qualified study physician
	Break (if needed)	~20-30	
2	Symbol Digit Modalities Test Stroop Word Reading Test MoCA	~20	Qualified study personnel
	Break (if needed)	~10	
3	Neuro-QoL Cognition Function Short Form EuroQol 5-Dimension, 5-Level Questionnaire (patient and companion) Health Utilities Index (companion: self and proxy) Patient/Companion-reported Global Impression—Severity Patient/Companion-reported Global Impression—Change	~30	Qualified study personnel
4	Roche HD mobile application ^a	~20	Qualified study personnel

MoCA=Montreal Cognitive Assessment; Neuro-QoL=Quality of Life in Neurological Disorders;
UHDRS=Unified Huntington's Disease Rating Scale

^a These assessments will take place only at Weeks 5 and 53.

Appendix 4: Clinical Assessments Order and Duration for Patients Enrolled after Implementation of Protocol Version 4 (cont.)

Table 4 Follow-Up Clinical Assessments at Weeks 13, 29, 45, 61, 77, and 93

Block	Assessments	Total Duration (minutes)	Site Staff Responsible
1 ^a	Apathy Evaluation Scale (patient and companion) Symptoms of Major Depressive Disorder Scale	~20	Qualified study personnel
	Break (if needed)	~10	
2	Huntington's Disease-Daily Activities Scale	~25	Qualified study physician

^a To be completed prior to safety assessments.

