- It has been clarified that all patients in the treatment period will discontinue study treatment and enter the early treatment termination (ETT) schedule. The previous version of the protocol already described the ETT schedule for following of individuals, for safety and efficacy outcomes, who have discontinued the study drug but not withdrawn consent for continued study participation (Sections 3.1.1, 4.2, and 4.6, and Figure 1 and 2). Additional clarification on visits and assessments required on the ETT schedule has been provided (Section 3.1.1.1, and Figure 3, and Appendices 1a and 1b).
- The ETT visit window has been extended from 28 (\pm 7 days) from last dose to within 56 days of the decision to discontinue study treatment (i.e., from 22 March 2021). This extension has been made to facilitate scheduling of the ETT visit using the existing planned visit schedule (Section 3.1.1.1, and Appendices 1a and 1b).

- It has been clarified that following the iDMC recommendation to discontinue study treatment dosing in this study, the Sponsor will be unblinded to treatment assignment, to allow for data analyses to occur, in order to enhance the understanding of RO7234292 effects and to inform RO7234292 program next steps (Sections 3.1.2, 4.2, and 4.5.9.22).
- End of study and length of study have been adjusted, as a result of all patients moving to the ETT schedule (Section 3.2).
- It has been clarified that patients should not perform any activity that is associated with a change in the ambient air pressure for at least 24 hours post lumbar procedure, irrespective if study treatment is administered or not (Section 4.5.5, Appendices 1a and 1b).
- As per protocol, individuals will have an LP at the ETT visit. Additional safety assessments including lumbar puncture and laboratory tests have been added to the end of treatment (EoT) assessment for ETT to ensure complete and adequate collection of follow-up safety outcomes (Section 4.5.5, Appendices 1a and 1b).
- Wording in Section 5.1.1 and Section 5.1.2 has been amended to be consistent with the latest available risk data as per the RO7234292 Investigator's Brochure Version 7.
- Adverse event reporting period has been clarified, as a result of all patients moving to ETT schedule and discontinuing study treatment (Sections 5.3.1 and 5.4.2.2).

TABLE OF CONTENTS

PROTOCOL AMENDMENT ACCEPTANCE FORM	14
PROTOCOL SYNOPSIS	15
1. BACKGROUND	28
1.1 Background on Huntington's Disease.....	28

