2.2 SAFETY OBJECTIVE

The safety objective for this study is to evaluate the safety and tolerability of RO7234292 compared with placebo on the basis of the following endpoints:

- Incidence and severity of adverse events, with severity determined according to the Adverse Event Severity Grading Scale (see [Table 4](#))
- Change from baseline in Montreal Cognitive Assessment (MoCA)

- Change from baseline in vital signs
- Change from baseline in ECG parameters
- Change from baseline in clinical laboratory results
- Proportion of patients with suicidal ideation or behavior, as assessed by Columbia-Suicide Severity Rating Scale (C-SSRS) score at each visit, including detailed focus on any individual cases identified as having severe ideation or behavior during the study conduct

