When applicable, study treatment administration will occur via a lumbar puncture using a needle inserted into the L3/L4 space, although placement at a different level (either in the space above or the space below) is allowed if patient anatomy or clinical judgment dictates. The left lateral position is mandatory in the first instance for the procedure for consistency of procedure practice across sites and within patients, unless patient-specific factors require use of the upright, sitting position or the physician/operator has pre-existing experience using LP/intrathecal bolus dosing in the sitting position and prefers the use of the upright sitting position, as guided by the patient, his or her judgment. Whichever position is used, once access is established to the IT space, the entire IT bolus procedure should be completed in the same position, to limit the risk of the needle losing position while the spinal needle is inserted. Subsequent LP administrations should occur using the same position.

Patients will be discouraged from resting supine after the lumbar puncture procedure and will be encouraged to mobilize immediately by walking around at a minimum and, if feasible, walking briskly for approximately 30 minutes, after which the postdose neurological examination can occur (*if study treatment was administered*). Patients should not perform any activity that is associated with a change in the ambient air pressure for at least 24 hours *post-LP procedure* (e.g., air travel, scuba diving, or hot air balloons).

Lumbar punctures will be performed as specified in the schedule of activities (see [Appendix 1](#)), with the last CSF sample obtained at the Week 101 end-of-treatment

visit. After discontinuation of study treatment, LPs will be performed at the ETT and EoT for ETT visits (see [Appendix 1a](#) and [Appendix 1b](#)). No study drug will be administered at these visits.

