6.7 SAFETY ANALYSES

The safety population (see Section [6.1](#)) will be the primary population for all analyses of safety data. Incorrect treatment assignments (patients who received a treatment different than their planned randomized treatment) will be summarized and the impact on the safety assessment will be discussed.

For all safety analyses, patients enrolled prior to implementation of the Version 4 of the protocol will be summarized separately.

All verbatim adverse event terms will be mapped to MedDRA thesaurus terms. The adverse event severity grading scale indicated in [Table 4](#) will be used for assessing adverse event severity. Laboratory values determined as an adverse event should be graded as per [Appendix 6](#), which is based on the NCI CTCAE (v5.0).

All safety data, including adverse events, laboratory tests, CSSR-S, MoCA, ECG, and vital signs will be reported in individual listings and summarized by treatment for each assessment time using descriptive statistics. For continuous variables, both the original value as well as the change from baseline will be reported.

The incidence of adverse events will be summarized on the basis of body systems and dictionary preferred terms. The incidence of adverse events by severity and relationship to study drug or study procedure and incidence of marked abnormal laboratory test results will be provided.

The iDMC will review safety data throughout the study. Analyses required for the iDMC data review will be performed as described in the iDMC Charter.

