- × CSF samples will be obtained at the Week 101 EoT, *Week 101 EoT for ETT, and ETT visits*, but no study drug will be administered.
- × Patients in Q16W arm will receive placebo at these visits.

^{aa} Medication (e.g., prescription drugs, over-the-counter drugs, vaccines, herbal or homeopathic remedies, nutritional supplements) used by a patient in addition to protocol-mandated treatment from screening to the study completion/discontinuation visit.

^{bb} After informed consent has been obtained but prior to initiation of study drug, only serious adverse events caused by a protocol-mandated intervention should be reported. After initiation of study drug, all adverse events will be reported until 5 months after the final dose of study drug. After this period, all deaths, regardless of cause, should be reported. In addition, the Sponsor should be notified if the investigator becomes aware of any serious adverse event that is believed to be related to prior study drug treatment.

^{cc} The DCL will be assessed at screening only (i.e., without the full TMS assessment). The TMS scale will be assessed (excluding the DCL) at all other timepoints.

^{dd} Excluding MRIs, which have a visit window of -14 to -7 days.

^{ee} During the treatment period, a safety follow-up telephone call will be conducted for the months in which no clinic visits are. A safety follow-up call will also be conducted approximately 2 months after the Week 101 visit. Telephone safety follow-up calls will assess any changes to ongoing adverse events or occurrence of new adverse events and changes to concomitant medication. Unscheduled visits can occur based on the outcome of this safety follow-up call.

Appendix 1b Schedule of Activities for Early Treatment Termination (Applicable to all Patients from 22 March 2021)

Visit	ETT ^a	FU Week 53 ^a	FU Week 69 ^a	EoT for ETT (Week 101) ^a	Safety Follow-Up Calls ^b
Month		13	17	25	
Window (days)	≤ 56 days after the decision to discontinue study treatment	(± 7)	(± 7)	(± 7) ^c	(± 7)
Vital signs ^d	x				
Complete physical examination ^e	x				
Neurologic examination ^f	x			x	
ECG ^g	x			x	
Hematology ^h	x			x	
Chemistry ⁱ	x			x	
Pregnancy test ^j	x			x	
Local INR and/or PT, aPTT, platelet count ^k	x			x	
Urinalysis ^l	x			x	
Plasma sample for PK	x				
Plasma sample for immunogenicity testing	x			x	
Plasma sample for biomarkers	x			x	
CSF sample for safety/biomarkers	x			x	
MRI ^m				x	
Independence Scale	x	x	x	x	
MoCA	x	x	x	x	

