AES = Apathy Evaluation Scale; CGI-C = Clinical Global Impression, Change; CGI-S = Clinical Global Impression, Severity; CrGI-C = Companion-Reported Global Impression, Change; CrGI-S = Companion-Reported Global Impression, Severity; CRQ = Companion-reported questionnaire; CSF = cerebrospinal fluid; C-SSRS = Columbia-Suicide Severity Rating Scale; cUHDRS = composite Unified Huntington's Disease Rating Scale; eCRF = electronic Case Report Form; EoT = end of treatment; EQ-5D-5L = EuroQol 5-Dimension, 5-Level Questionnaire; ETT = early treatment termination; FA = Functional Assessment; FU = follow-up; HD = Huntington disease; HD-CIAOS = Huntington's Disease Companion-Reported Irritability and Angry Outbursts Scale; HUI = Health Utilities Index; LP = lumbar puncture; MoCA = Montreal Cognitive Assessment; MRI = magnetic resonance imaging; Neuro-Qol = Quality of Life in Neurological Disorders; PGI-C = Patient Global Impression, Change; PGI-S = Patient Global Impression, Severity; PK = pharmacokinetic; RBR = Research Biosample Repository; SDMT = Symbol Digit Modalities Test; SMDDS = Symptoms of Major Depressive Disorder Scale; SWR = Stroop Word Reading; TFC = Total Functional Capacity Scale; TMS = Total Motor Score; UHDRS = Unified Huntington's Disease Rating Scale.

Notes: Unscheduled safety assessments (MRI, ECG, safety laboratory assessments, vital signs) can be performed if clinically indicated.

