- ^e The complete physical examination should include an evaluation of the head, eyes, ears, nose, and throat, and the cardiovascular, dermatologic, musculoskeletal, respiratory, gastrointestinal, and neurologic systems; genitourinary examinations may be performed if clinically indicated. Changes from baseline abnormalities should be recorded in patient notes. New or worsened clinically significant abnormalities (i.e., beyond expected variation or normal age-related change) should be recorded as adverse events on the Adverse Event eCRF.
- ^f A neurologic examination (including fundoscopy) should include assessment of mental status, level of consciousness, cranial nerve function, motor function, sensory function, reflexes, gait, and coordination. The neurologic examinations should be conducted in the same manner on each occasion to ensure comparability to previous examinations. At visits when an LP is performed and study treatment is not administered, the neurological examination should be performed prior to the LP. Changes from baseline abnormalities should be recorded in patient notes. New or worsened clinically significant abnormalities (i.e., beyond expected variation or normal age-related change) should be recorded as adverse events on the Adverse Event eCRF.
- ^g Triplicate ECG are to be performed within approximately 5 minutes of each other, after the patient has been in a supine position for approximately 10 minutes. ECGs for each patient should be obtained from the same machine whenever possible. The ECG should be performed prior to any blood draws and before the lumbar puncture.
- ^h Hematology includes WBC count, RBC count, platelet count, hemoglobin, hematocrit, differential count (neutrophils, eosinophils, basophils, monocytes, lymphocytes).
- ⁱ Serum chemistry panel: includes bicarbonate or total carbon dioxide (if considered standard of care for the region), sodium, potassium, chloride, glucose, BUN or urea, creatinine, total protein, albumin, phosphorus, calcium, total and direct bilirubin, ALP, ALT, AST, uric acid, gamma-glutamyl transferase, and CPK.
- ^j Urine pregnancy tests will be performed at specified visits. If a urine pregnancy test is positive, it must be confirmed by a serum pregnancy test.

Appendix 1b: Schedule of Activities for Early Treatment Termination (Applicable to all Patients from 22 March 2021) (cont.)

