^k Prior to performing each scheduled lumbar puncture, local laboratory analysis of coagulation factors (INR and/or PT, aPTT) and platelets must be conducted and the results reviewed. Collection for these local laboratory tests may occur at any time in the 72 hours prior to the lumbar puncture. The lumbar puncture should be performed at approximately the same time at each visit (ideally in the morning between 8:00 a.m. and 12:00 noon or in the early afternoon between 12:00 noon and 3:00 p.m.) to minimize potential diurnal variation of CSF parameters. CSF fluid (20 mL) is to be collected for analyses using a lumbar puncture collection kit. If there are difficulties in collecting 20 mL of CSF fluid, a minimum of 5 mL should be collected over a maximum of 60 minutes, once CSF flow has been established. A 24G atraumatic needle, as specified in the LP procedure and CSF collection guidelines, should be used. Depending on institutional guidelines, local anesthesia should be used for the procedure. Sedation may not be used. Spinal ultrasound may be used for the lumbar puncture procedure if deemed necessary, but is not required. Ultrasound guidance may be used if attempts at lumbar puncture without imaging are unsuccessful, if it is local practice to use ultrasound, or if institutional guidelines dictate use of ultrasound with each lumbar puncture. Patients will be discouraged from resting supine after the lumbar puncture procedure and will be encouraged to mobilize immediately by walking around at a minimum and, if feasible, walking briskly for approximately 30 minutes. Patients should not perform any activity that is associated with a change in the ambient air pressure for at least 24 hours post-LP procedure (e.g., air travel, scuba diving, or hot air balloons). In the case of a failed CSF collection procedure (e.g., due to an inadequate establishment of access to the IT space), a second attempt may occur up to 7 days after the originally scheduled attempt. For this additional visit, safety and tolerability evaluations on the day of LP administration will be performed, including a pre-procedure neurological examination, vital signs, and a review of adverse events and concomitant medication. If the second attempt occurs more than 3 days after the first attempt, local laboratory analysis of coagulation factors (INR and/or PT, aPTT) and platelets need to be conducted again and results reviewed prior to the LP attempt.

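### Vital signs are the one Section 2.2 safety endpoint with no scheduled value at the Week 101 visit for patients on the early-termination schedule; marking them there is a cheap, minor improvement

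*Protocol*

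**What the plan says.** Section 2.2 lists six safety endpoints, one of which is "Change from baseline in vital signs". Section 6.7 plans the matching output: "ECG, and vital signs will be reported in individual listings and summarized by treatment for each assessment time using descriptive statistics".

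After the stop on 22 March 2021, patients who stay in the study follow Appendix 1b. Its visits are ETT, Week 53, Week 69 and Week 101 (called EoT for ETT), plus safety calls. The vital-signs row has one mark, at ETT. Section 4.5.5 states: "After discontinuation of study treatment, LPs will be performed at the ETT and EoT for ETT visits". The Version 6 summary of changes counts the puncture and the laboratory tests among the safety assessments that, as it puts it, "have been added to the end of treatment (EoT) assessment for ETT to ensure complete and adequate collection of follow-up safety outcomes".

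Three other parts of Appendix 1b bear on the point:

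- Footnote k covers a second attempt, up to 7 days later, after a failed CSF collection: "For this additional visit, safety and tolerability evaluations on the day of LP administration will be performed, including a pre-procedure neurological examination, vital signs".
- The notes under the table allow further checks: "Unscheduled safety assessments (MRI, ECG, safety laboratory assessments, vital signs) can be performed if clinically indicated".
- Footnote g sets the order on the day: "The ECG should be performed prior to any blood draws and before the lumbar puncture".

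**The concern.** Version 6 strengthened the Week 101 visit so that off-treatment safety follow-up would be complete, and it made that visit a lumbar puncture visit. Vital signs are a named safety endpoint, and the protocol treats them as a puncture-day check when the procedure is repeated. Yet they are not scheduled at this visit.

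Two things are at stake, both modest. First, the by-arm summary of vital signs for these patients ends at the ETT visit, while every other Section 2.2 endpoint continues to Week 101. Section 1.3 says dosing stopped on unfavorable safety and efficacy trends in the treatment arms, and patients were kept in the study for follow-up of both. Second, blood pressure, temperature and respiratory rate are not scheduled before the Week 101 puncture, although Section 5.1.1 lists unstable cardiorespiratory status as a contraindication and Section 5.1.1.3 lists pyrexia among the signs of meningitis.

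**Working it through.** No power or error-rate calculation applies. The check has three parts.

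**1. Reading Appendix 1b.** Each row compared below has five cells (ETT, Week 53, Week 69, Week 101, safety calls), so a broken table does not explain the blank.

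| Row | Marked at |
|---|---|
| Vital signs | ETT |
| Complete physical examination | ETT |
| Neurologic examination | ETT, Week 101 |
| ECG | ETT, Week 101 |
| Lumbar puncture | ETT, Week 101 |

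Vital signs are therefore scheduled at 1 of the 2 puncture visits, and neurologic examination and ECG at 2 of 2.

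**2. The Section 2.2 endpoints against the Week 101 column.**

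| Section 2.2 endpoint | Marked at Week 101 in Appendix 1b |
|---|---|
| Adverse events | yes |
| MoCA | yes |
| Vital signs | no |
| ECG | yes |
| Laboratory results | yes (hematology, chemistry, urinalysis) |
| C-SSRS | yes |

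That is 5 of 6. Section 4.5.4 says how vital signs are measured but gives no timing, so it does not fill the gap.

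**3. Length of the gap.** The ETT visit may fall 0 to 56 days (0 to 8 weeks) after the decision to stop. Hence

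weeks without scheduled vital signs = 101 − (week at the stop + 0 to 8).

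| Week at the stop (example) | Shortest | Longest |
|---|---|---|
| 29 | 101 − 37 = 64 | 101 − 29 = 72 |
| 61 | 101 − 69 = 32 | 101 − 61 = 40 |
| 85 | 101 − 93 = 8 | 101 − 85 = 16 |
| 93 | 101 − 101 = 0 | 101 − 93 = 8 |

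The 7-day window either side of Week 101 moves each figure by at most 1 week. The starting weeks are assumptions, since the protocol does not give the distribution of patients over study weeks on 22 March 2021.

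**Appendix 1a** also has a column for this visit, but its columns are out of line in the available text. Its vital-signs row holds 16 marks against 17 in the neurologic-examination row. That fits one visit being left out but does not show which one, so nothing here depends on it.

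**The case against.** The strongest reply is that nothing in the protocol is contradicted, and that is right. Section 2.2 gives the vital-signs endpoint no timepoint, whereas the C-SSRS endpoint in the same list is tied to every visit. Section 6.7 summarises at whatever times are assessed, so it can be carried out as written. A reader might infer that footnote k conflicts with the table. It does not: it sets its own list of checks for a separate, unplanned visit.

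The reduced set may also be deliberate. The complete physical examination is likewise marked at ETT only, and the Version 6 summary names the puncture and laboratory tests, not vital signs. This has some force. However, the physical examination is not a Section 2.2 endpoint and footnote k does not ask for it, and no reason is given for leaving vital signs out.

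A reader might also infer that the Week 101 puncture goes ahead without safety checks. It does not. ECG, neurologic examination and coagulation tests all precede it, no drug is given, adverse events are collected at least to that visit (Section 5.3.1), and Section 5.3.5.6 has clinically significant vital-sign abnormalities reported as adverse events. What these do not supply is a planned reading of blood pressure, temperature and respiratory rate.

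The allowance for unscheduled readings does not close the gap for analysis. Patients measured because something seemed wrong are a selected group and cannot stand in for a by-arm summary. The same note also names MRI, ECG and laboratory tests, and all three are scheduled at Week 101 as well.

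**Conclusion.** The point holds as a minor, cheap improvement. For patients who consented to Version 6 and follow Appendix 1b, change from baseline in vital signs is the only one of six Section 2.2 safety endpoints with no scheduled value at Week 101. Efficacy endpoints, type I error, power and dosing are unaffected.

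The conclusion rests on Appendix 1b alone. The gap lengths are illustrations that run from 64 to 72 weeks down to 0 to 8 weeks. A reader might take the longest as typical, but the protocol gives no basis for that. Nor do the documents support calling this an internal contradiction or a planned analysis that cannot be done. By-arm vital signs remain scheduled at the ETT visit, close to the end of dosing for patients stopped by the March 2021 decision. What is lost is the unselected reading at the end of off-treatment follow-up and a planned check before the last puncture.

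**What to change.** Mark vital signs in the Week 101 (EoT for ETT) column of Appendix 1b, and add to footnote d that at this visit they are taken before the lumbar puncture. Make the matching column of Appendix 1a agree. The statistical text needs no change, because Section 6.7 would pick up the added assessment time as it stands.

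The cost is one table mark, a short footnote addition and a cross-check of Appendix 1a, plus a few minutes per patient at a visit already attended for ECG, blood samples and the puncture.
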